Randomization to study method will occur after completion of all intake forms and consent, immediately before the pill is to be taken, thus reducing the possibility of withdrawal after randomization. Primary outcome measures and most secondary outcome measures will be assessed immediately before, during or after the abortion procedure, thus any loss to follow-up will be limited to those who consent to, but change their mind while waiting for their procedure. Based on current clinical practice at this clinic, withdrawal after consent is extremely rare. Our secondary outcomes assessed post-operatively after discharge will be collected via the phone. We will maximize completion of these assessments through the following steps: participants will be told beforehand about the telephone contact following the procedure, a cellular telephone number will be collected and tested at the clinic, a secondary phone number and email will be collected as a backup, participants will be given a contact number for the study coordinator should they have any challenges with receiving a phone calls, and participants will receive an additional \$10 sent to their gift-card following the completion of their phone assessment.

Data Collection/Outcome measurements:

Outcome measures and baseline variables are described in Table 1.

Primary study outcome

Our primary outcome measure will be pain score using an 100-mm visual analog scale (VAS) measured 5 minutes after removal of the speculum.

Secondary Outcomes:

We will also be measuring pain on the 100-mm VAS preoperatively immediately prior to the procedure, after the procedure, 10 minutes and 30 minutes following the procedure and at discharge. Nausea, using a VAS, and vomiting will be assessed preoperatively immediately prior to the procedure and post operatively at 10 minutes, 30 minutes and at discharge. Anxiety prior to the procedure will be measured using the preoperative state trait anxiety inventory. Side effects will be assessed using a checklist prior to discharge. We will also be contacting participants on post-operative day 1 to assess pain, nausea, vomiting, side effects and general satisfaction with the procedure (on a 5-point scale). The quantity and type of medications used perioperatively and post-operatively including medications used at home in the 24 hours post-operatively will be abstracted from the clinical record and assessed on the phone.

Baseline Characteristics and covariates:

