An adverse event (AE) is defined as any health-related reaction, effect, toxicity or abnormal laboratory result that a study participant experiences during the course of the study, irrespective of relationship to the study intervention. This includes changes in a participant's condition that have or could have a deleterious effect on a participant's health or well-being. A serious adverse event (SAE) is defined as any experience that is fatal or life-threatening, requires

in-patient hospitalization or prolongation of an existing hospitalization, or results in a persistent or significant disability or incapacity.

This study uses an additional medication for pain control in the setting of outpatient abortion. These activities are not anticipated to be associated with any deleterious impact on participants' health or well-being beyond the risks associated with the abortion procedure. AEs will be managed according to good clinical practice and the judgment of the on-site physician. All clinical and laboratory AEs will be followed-up closely by study staff. Any SAEs will be expeditiously reported to the principal investigators, via a designated SAE form. Notification and submission of SAE forms should occur within 48 hours of the site awareness of the SAE. The PI will then make the final independent judgment as to the severity, relatedness, and anticipated or unanticipated nature of the SAE and finalize the Human Subjects Adverse Event Report Form. If the event is determined to be serious, unanticipated, and the relationship is anything other than probably or definitely not related, then the PI will report the event within 48 hours and submit the required forms to the IRB at Duke. Thus, all anticipated SAEs that are at least possibly related to study intervention and all deaths that are at least possibly related to study intervention will be submitted to the Duke IRB.

The study may be discontinued at any time by an IRB at a participating institution or the Office for Human Research Protection. We will additionally have a medical monitor to review any adverse event and periodically review side effects to see if there are an increased number of events than anticipated by routine clinical care. If any suspicion for increased risk exists, study allocation may be revealed for a preliminary analysis and if related to the study intervention, the study could be prematurely ended.

Data Monitoring Committee/Study Termination

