ANXIOUS**4. Make a hash mark on the line to indicate how much nausea you are currently experiencing.**NO
NAUSEA _____WORST NAUSEA
I HAVE EVER HAD5. Have you vomited since you had your procedure? ₀ NO ₁ YES

SIDE EFFECTS: Do you have any of the following?

Dizziness	 ₀ NO  ₁ YES, mild  ₂ YES, moderate  ₃ YES, severe
Ataxia (lack of muscle control)	 ₀ NO  ₁ YES, mild  ₂ YES, moderate  ₃ YES, severe
Somnolence (sleepiness or drowsiness)	 ₀ NO  ₁ YES, mild  ₂ YES, moderate  ₃ YES, severe
Asthenia (weakness, lack of energy)	 ₀ NO  ₁ YES, mild  ₂ YES, moderate  ₃ YES, severe
Headache	 ₀ NO  ₁ YES, mild  ₂ YES, moderate  ₃ YES, severe
Amblyopia (vision in one eye reduced/lazy eye)	 ₀ NO  ₁ YES, mild  ₂ YES, moderate  ₃ YES, severe

Post- anesthetic alдрete recovery score : modified Criteria	Points
Oxygenation	
SpO ₂ > 92% on room air	2
SpO ₂ > 90% on oxygen	1
SpO ₂ < 90% on oxygen	0
Respiration	
Breathes deeply and coughs freely	2
Dyspneic, shallow or limited breathing	1
Apnea	0
Circulation	
BP +/- 20% of normal	2
BP +/- 20-50% of normal	1
BP > 50% of normal	0
Consciousness	
Fully awake	2
Arousable on calling	1
Not responsive	0
Activity	
Moves all extremities	2
Moves two extremities	1
No movement	0

30-Minute Post Op Assessment

Time: ____ : ____ AM/PM

1. Make a hash mark on the line to indicate the worst pain you have felt up to this point today.NO
PAIN _____WORST PAIN
IN MY LIFE**2. Make a hash mark on the line to indicate how much pain you are currently in.**NO
PAIN _____WORST PAIN
IN MY LIFE**3. Make a hash mark on the line to indicate how much anxiety you are currently experiencing.**NO
ANXIETY _____EXTREMELY
ANXIOUS**4. Make a hash mark on the line to indicate how much nausea you are currently experiencing.**NO
NAUSEA _____WORST NAUSEA
I HAVE EVER HAD

4. Have you vomited since you had your procedure?

 ₀ NO ₁ YES

Discharge Assessment

Time: ____ : ____ AM/PM

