1. Make a hash mark on the line to indicate the worst pain you have felt up to this point today.

NO
PAIN _____

WORST PAIN
IN MY LIFE

2. Make a hash mark on the line to indicate how much pain you are currently in.

NO
PAIN _____

WORST PAIN
IN MY LIFE

3. Make a hash mark on the line to indicate how much anxiety you are currently experiencing.

NO
ANXIETY _____

EXTREMELY
ANXIOUS

4. Make a hash mark on the line to indicate how much nausea you are currently experiencing.

NO
NAUSEA _____

WORST NAUSEA
I HAVE EVER HAD

5. Have you vomited since you had your procedure? ₀ NO ₁ YES

Post- anesthetic Aldrete recovery score Modified Criteria [2]	Points
Oxygenation SpO ₂ > 92% on room air SpO ₂ > 90% on oxygen SpO ₂ < 90% on oxygen	2 1 0
Respiration Breathes deeply and coughs freely Dyspneic, shallow or limited breathing Apnea	2 1 0
Circulation BP +/- 20% of normal BP +/- 20-50% of normal BP > 50% of normal	2 1 0
Consciousness Fully awake Arousable on calling Not responsive	2 1 0
Activity Moves all extremities Moves two extremities No movement	2 1 0

24 hours post-procedure measures

Time: _____ AM/PM

Did you fill any pain medication prescription? ₀ NO ₁ YES

Have you taken any medication since you left the clinic for pain, nausea, vomiting or any other medication

Have you vomited since you left the clinic? NO YES, number of times _____

Overall satisfaction with experience 0-10 scale (0 = very dissatisfied; 10 = very satisfied): _____

Quality of Recovery Survey[3]

Part A

	How have you been feeling in the last 24 hours? (0 to 10, where 0 = none of the time [poor] and 10 = all of the time [excellent])	0-10
1	Able to breathe easily	
2	Been able to enjoy food	
3	Feeling rested	
4	Have had a good sleep	
5	Able to look after personal toilet and hygiene unaided	
6	Able to communicate with family and friends	
7	Getting support from hospital doctors and nurses	
8	Able to return to work or usual home activities	
9	Feeling comfortable and in control	
10	Having a feeling of general well-being	

Part B

	Have you had any of the following in the last 24 hours? (0 to 10, where 10= none of the time [excellent] and 0 = all of the time [poor])	0-10
1	Moderate pain	
2	Severe pain	
3	Nausea or vomiting	

4	Feeling worried or anxious	
5	Feeling sad or depressed	

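### The draft 24-hour form asks about none of the six checklist symptoms and scores satisfaction 0-10, although the protocol promises side effects and a 5-point scale on the day-1 call

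*Combined protocol and SAP*

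**What the plan says.** Secondary Aims includes evaluating the side effects or adverse events of gabapentin in this setting. The Secondary Outcomes section gives two occasions for doing so. In the clinic, "Side effects will be assessed using a checklist prior to discharge". The next day, staff will be "contacting participants on post-operative day 1 to assess pain, nausea, vomiting, side effects and general satisfaction with the procedure (on a 5-point scale".

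The Draft Questionnaire carries one side-effect checklist, on the 10-minute post-operative page. It opens "SIDE EFFECTS: Do you have any of the following" and grades six symptoms from none to severe: dizziness, ataxia, somnolence, asthenia, headache and amblyopia.

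The 24-hour page asks whether a pain prescription was filled, then "Have you taken any medication since you left the clinic for pain, nausea, vomiting or any other medication", then "Have you vomited since you left the clinic" (with a count), then "Overall satisfaction with experience 0-10 scale (0 = very dissatisfied; 10 = very satisfied". The 15-item Quality of Recovery survey follows.

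The Adverse events section defines an adverse event as "any health-related reaction, effect, toxicity or abnormal laboratory result that a study participant experiences during the course of the study" and says the study will "have a medical monitor to review any adverse event and periodically review side effects". The Analytic Plan assigns chi-square tests to categorical secondary outcomes and t-tests to continuous ones.

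**The concern.** The protocol text and the form meant to carry it out disagree on two of the five things the day-1 call should measure. Side effects are promised and not asked about, beyond nausea and vomiting. Satisfaction is asked, but on a different scale.

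The side-effect half matters more, because it bears on a stated aim. The one checklist is worded in the present tense, so it records what a woman feels about 10 minutes after the procedure. The day-1 call is the only planned contact after discharge. Symptoms not asked about on that call cannot be recovered reliably later, and any comparison of tolerability by arm would in effect stop at the recovery room.

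Satisfaction serves no stated aim. However, the scale decides which test applies under the Analytic Plan, and it should be fixed before data entry screens are built.

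**Working it through.** No figure in the plan needs to be reproduced for this point; the check sets the texts side by side.

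**1. Day-1 commitments against the draft 24-hour page**

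| Promised in Secondary Outcomes | On the draft 24-hour page | Result |
|---|---|---|
| Pain | Two Quality of Recovery ratings (moderate pain, severe pain) | Some item present |
| Nausea | One combined nausea-or-vomiting rating over the last 24 hours | Partial; not separable from vomiting, and the period may include clinic time |
| Vomiting | Yes/no with count since leaving the clinic, plus the combined rating | Present |
| Side effects, listed separately | No checklist and no open question | Absent |
| Satisfaction, 5-point | 0-10 score | Present on another scale: 11 possible values against 5 |

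**2. Item count.** Prescription filled, medication taken, vomiting and satisfaction make 4 items. Quality of Recovery Part A has 10 and Part B has 5. The total is 4 + 10 + 5 = 19. Items naming any of the six checklist symptoms: 0 of 19.

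**3. Side-effect assessments promised against those on the form.** Two are promised: a checklist before discharge, and the day-1 call. The 10-minute checklist meets the first. Nothing on the form meets the second, so 1 of 2 is covered.

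**4. What could still record the six symptoms after 10 minutes**
- The discharge page repeats the modified Aldrete score. Its consciousness and activity items are staff ratings from 0 to 2. They could register marked sedation or loss of movement, but not headache, visual change or mild dizziness, and they end at discharge.
- Quality of Recovery items on feeling rested, sleep, self-care and return to usual activity overlap with somnolence and asthenia. They do not identify either symptom.
- The adverse-event definition is broad enough to include all six. The section specifies no prompted question, so capture depends on what a participant volunteers.

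**5. Timing of the only checklist.** The protocol gives dosing 1 to 2 hours before the procedure, about 2 hours to peak concentration, and a half-life of 5 to 7 hours. Procedure length is not stated; I assume 5 to 20 minutes. The checklist then falls at 60 + 5 + 10 = 75 to 60 + 20 + 10 = 90 minutes after a dose taken 1 hour before, and at 120 + 5 + 10 = 135 to 120 + 20 + 10 = 150 minutes after a dose taken 2 hours before. It can therefore come before or after the stated peak, and on the stated half-life exposure continues well beyond it.

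**6. Effect on the primary analysis.** None. The primary outcome is pain 5 minutes after speculum removal. The planned 96 women rest on a 15 mm difference and a 26 mm standard deviation: n per arm = 2 × (1.96 + 0.842)² × 26² / 15² ≈ 47.2, rounded up to 48, or 96 in total (two-sided 0.05 assumed, normal approximation). The 24-hour items do not enter that calculation.

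**The case against.** The strongest objection is that the form is headed as a draft and that Table 1, which the protocol cites for its outcome measures, is not in the available text. The operations manual is not available either. The missing items may exist elsewhere. This stands as a condition on the consequence: the texts visibly conflict, but the loss of data follows only if the draft is used as it is.

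A reader might infer three stronger things that the documents do not support:
- *That the 24-hour page has no side-effect item at all.* The protocol itself lists nausea and vomiting among gabapentin's side effects, and both are asked about in some form. What is missing is any question on the other symptoms.
- *That symptoms after 10 minutes would reach the data only through unprompted reports.* The discharge Aldrete ratings and the Quality of Recovery items overlap in part. They are too coarse or too non-specific to replace a symptom question, but they exist.
- *That nausea is fully covered on day 1.* It is asked about only in a combined item.

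It can also be said that this is a single dose, and that the protocol associates most listed effects with chronic use. That lowers the expected number of events. It does not remove the commitment to ask. Finally, the protocol ties the checklist only to the period before discharge, so the day-1 text does not strictly require the full six items. That is correct, and an open question would meet the wording.

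**Conclusion.** The inconsistency is real and moderate in weight. Secondary Outcomes and the draft 24-hour page disagree on side effects other than nausea and vomiting (promised, with 0 of 19 items naming any of the six symptoms) and on the satisfaction scale (5-point against 0-10). If the draft is used unchanged, the side-effect aim cannot be addressed by a systematic comparison of arms from 10 minutes to 24 hours. That consequence assumes that neither Table 1 nor the final form contains the items. The satisfaction mismatch is minor, and the primary outcome and the sample size of 96 are untouched.

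**What to change.** Reconcile the Secondary Outcomes section with the 24-hour page before the database is built.

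- Add a structured side-effect question to the day-1 call. The simplest choice is the existing six-item checklist, reworded to cover the time since leaving the clinic, as the form's vomiting and medication questions already do. The minimum is one open side-effect question.
- State that the 24-hour responses will be reported by arm.
- Use one satisfaction scale in the protocol and on the form, and name its test under the Analytic Plan: chi-square if treated as categorical, t-test if treated as continuous.

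The cost is a form and database edit and a few minutes on a call already planned. If Table 1 or the final form already contains these items, only the texts need to be aligned.

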We will collect baseline demographics, medical history (gravidity, parity, prior abortions (medical and surgical), gestational age, drug and alcohol use, psychiatric or sexual assault history), medications used at home and given at the clinic preoperatively, indication for procedure (personal/social, fetal or maternal health)).

Study Size and Power:

We will enroll a total of 96 women. Assuming a standard deviation of 26 mm on the 100-mm visual analog scale (VAS), based on prior studies, this will provide us with an 80% power, using a p-value of 0.05, to detect a 15 point difference in pain among all participants. A difference of 15-20 mm has been assessed to be clinically meaningful in prior studies. Given that our primary outcome will be measured immediately after the procedure, our loss to follow-up will be minimal. A 100-mm pain visual analog scale has been shown to be useful for the evaluation of pain in prior pain abortion research [5, 6] with a mean standard deviation in previous studies of approximately 26 mm [5]. We are assuming no loss-to-follow-up as our primary outcome will be measured at the time of the procedure.

Data Management and Analysis

Data Management:

Prior to study initiation, a database will be developed using a web-based password-protected relational database (REDCap). All data will be collected will be recorded on clinical research forms (CRFs) and entered into the database at the end of each day. All CRF source documents will be filed and stored for future reference. See monitoring and oversight section below for further details on procedures and protections.

Analytic Plan:

We will compare groups on the primary continuous outcome measure (pain score on 11-point VAS) using T-tests. Chi-square and T-tests will be used to evaluate secondary outcomes for categorical and continuous variables, respectively. Baseline characteristics will be evaluated for potential interaction or confounding with primary and secondary outcomes.

Upon study completion at each site for the prospective meta-analysis, data from each site will contribute to the final meta-analysis using criteria outlined in the Cochrane Handbook for Systematic Reviews of Interventions. Site RCT publications will mention contribution to this PMA. Subgroup analyses will address gabapentin adjunct to local anesthesia and moderate sedation, as well as by specified population characteristics and gestational age.

Ethical Concerns

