Strengths of this study include its linkage with 4 other sites to be included in a prospective meta-analysis. The PMA design can bypass some of the logistical challenges of a multisite RCT. The PMA design allows each site to operate independently, thus reducing impact of delays from one site. Sharing of resources, such as study drug and placebo, and patient gift cards, will save time and money. Limitations of this study is that we are only looking will only be able to evaluate the impact of gabapentin within the timeframe 1-2 hours preoperatively for surgical procedures. Future research may be useful in evaluating the utility of Gabapentin if given 1 day prior to the procedure, at time of laminaria placement for 2 day procedures, or if given prior to medication abortion.

Gabapentin is low-cost and effective in perioperative settings, and may be an effective adjunctive therapy for surgical abortion. PMA methodology will evaluate the potential effect of adding gabapentin to different pain control regimens and among different patient populations, maximizing external validity. We anticipate several publications and presentations from individual sites as well as from the combined in the PMA to allow for dissemination of our findings. Further, we aim to leverage the developed PMA infrastructure to apply for future large research studies in abortion care, providing an innovative and feasible approach for developing generalizable research and to target low prevalent groups.

Problems Anticipated

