You answer the question by making a hash mark on the line according to how much you like or dislike Oreo cookies.

If you liked Oreo cookies a lot, then you might make a hash mark on the line like so:

very
little

very
much

If you liked Oreo cookies more than life itself(!), then you might make a hash mark on the line like so:

very little _____ |

very
much

If you hated Oreo cookies, then you might make a hash mark like so:

very
little

very
much

If you thought Oreo cookies were just "OK," then you might make a hash mark like so:

very
little

very
much

The idea is that if you like Oreo cookies, you make a hash mark on the line closer to the phrase "very much;" the closer you make the hash mark, the more you are saying you like Oreo cookies. If you don't like Oreo cookies, you make a hash mark on the line closer to the phrase "very little;" the closer you make the hash mark, the more you are saying you don't like Oreo cookies.

1. Make a hash mark on the line to indicate how nervous you feel about the surgery you are about to have.

NOT
NERVOUS _____

VERY NERVOUS

2. Make a hash mark on the line to indicate how nervous you feel about the pain you will experience during your procedure.

NOT
NERVOUS _____

VERY
NERVOUS

3. Make a hash mark on the line to indicate how much pain you expect to have during your abortion procedure.

NO
PAIN _____

WORST PAIN
IN MY LIFE

4. Make a hash mark on the line to indicate how much pain you have waiting for your procedure to start.

NO
PAIN _____

WORST PAIN
IN MY LIFE

5. Make a hash mark on the line to indicate how much nausea you currently have

NO
NAUSEA _____

WORST NAUSEA
I HAVE EVER HAD

Have you vomited since you received your study medication?

NO YES

State Trait Anxiety Inventory[1]

Read each statement and select the appropriate response to indicate how you feel right now, that is, at this very moment. There are no right or wrong answers. Do not spend too much time on any one statement but give the answer which seems to describe your present feelings best.

		Not at all	A little	Somewhat	Very much so
1	I feel calm	1	2	3	4
2	I feel secure	1	2	3	4
3	I feel tense	1	2	3	4
4	I feel strained	1	2	3	4
5	I feel at ease	1	2	3	4
6	I feel upset	1	2	3	4
7	I am presently worrying over possible misfortunes				
8	I feel satisfied	1	2	3	4
9	I feel frightened	1	2	3	4
10	I feel uncomfortable	1	2	3	4
11	I feel self confident	1	2	3	4
12	I feel nervous	1	2	3	4
13	I feel jittery	1	2	3	4
14	I feel indecisive	1	2	3	4

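### Does calling the primary pain score an 11-point VAS in the Analytic Plan leave the primary analysis unclear?

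*Combined protocol and SAP*

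**What the plan says.** The Analytic Plan (under Data Management and Analysis) says: "We will compare groups on the primary continuous outcome measure (pain score on 11-point VAS) using T-tests".

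The other places that bear on the scale of the primary outcome are these:

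- The paragraph that defines the primary endpoint states: "Our primary outcome measure will be pain score using an 100-mm visual analog scale (VAS) measured 5 minutes after removal of the speculum".
- For the other pain assessments, the list of secondary endpoints states: "We will also be measuring pain on the 100-mm VAS preoperatively immediately prior to the procedure", and then at the later clinic-day times.
- Study Size and Power: "Assuming a standard deviation of 26 mm on the 100-mm visual analog scale (VAS), based on prior studies", with a 15-point difference to be detected, followed by "A difference of 15-20 mm has been assessed to be clinically meaningful in prior studies".
- Draft Questionnaire: on the clinic-day forms, pain intensity is a hash mark on an unnumbered line running from no pain to the worst pain of the woman's life. An example is preoperative item 4: "Make a hash mark on the line to indicate how much pain you have waiting for your procedure to start". The form text prints no line length.

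The section on outcome measurements also points to a table: "Outcome measures and baseline variables are described in Table 1". That table was not in the text available for this review.

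**The concern.** The sentence that pre-specifies the one primary test ought to name the variable that is recorded. Here it names an 11-point scale, while the outcome is defined and powered in millimetres. Taken literally, it could mean that a 0-10 rating is the primary variable, or that the marks are to be collapsed to whole points before the test. The reported mean difference would then be ten times smaller in number (15 mm becomes 1.5 points), and this site's results are meant to be pooled with those of others: "Strengths of this study include its linkage with 4 other sites to be included in a prospective meta-analysis".

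A second uncertainty sits beside it. The 5-minute form has two pain lines, worst pain so far that day (item 1) and current pain (item 2), and the outcome definition speaks only of a pain score. If the choice were truly open, it could be made after the data were seen.

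**Working it through.** **1. Does the plan's own arithmetic identify the scale?** Inputs from Study Size and Power: difference 15, SD 26 mm, alpha 0.05, power 80%, total 96, no loss to follow-up. Allocation is equal (Recruitment). The plan does not say whether the test is two-sided; two-sided is assumed.

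- n per arm = 2 × (1.960 + 0.842)² × (26/15)² = 2 × 7.849 × 3.004 = 47.2, rounded up to 48, so 96 in total. This reproduces the plan's figure.
- Power at 48 per arm: 15 / (26 × √(2/48)) = 15 / 5.307 = 2.826, and Φ(2.826 − 1.960) = 0.807. With the noncentral t distribution it is 0.799.
- A one-sided test would need 38 per arm, 76 in total. That does not match, so the two-sided assumption is sound.

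An 11-point scale runs from 0 to 10, so the largest possible difference between two means is 10. A difference of 15 points can exist only on the 100-mm scale.

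**2. Would the label change the test?** Dividing every score by 10 divides the difference and the SD by 10:

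- 100-mm scale: 15/26 = 0.577 SD
- 0-10 scale: 1.5/2.6 = 0.577 SD

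The t statistic, p-value, sample size and power are identical. Only the unit of the estimate differs.

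**3. What if marks were also rounded to whole points?** No part of the protocol calls for this, so it is only a bound. Rounding adds a variance of about 1/12: SD = √(2.6² + 1/12) = √6.843 = 2.616. Noncentral-t power is then 0.794 against 0.799, a loss of about half a percentage point, and the normal formula still gives 48 per arm.

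**4. Is there an 11-point pain item that could be mistaken for the primary score?** The 0-10 items are on the 24-hour form: overall satisfaction and the recovery survey. The survey's two pain items ask how much of the last 24 hours was spent in moderate or severe pain. None of these can be a score taken 5 minutes after speculum removal.

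**5. Which 5-minute line is primary?** Secondary Outcomes and the primary definition together give six clinic-day pain times: before the procedure, immediately after, 5, 10 and 30 minutes, and discharge.

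| Item | Where asked | Count |
|---|---|---|
| Current pain | Preoperative item 4; immediate item 5; item 2 at 5, 10, 30 minutes and discharge | 6 of 6 |
| Worst pain so far | Item 1 at 5, 10, 30 minutes and discharge | 4 of 6 |

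Only current pain forms one series over all six. Pain during suction also has its own intraoperative line. The count covers the clinic day only: pain is also to be assessed on day 1, and the 24-hour form has no current-pain line.

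**The case for a change.** The best case for a change is that it costs one phrase and touches the most important sentence in the analysis section. That sentence names a variable the trial does not record, units matter when results are pooled, and the Primary Aim speaks of pain during aspiration, which leaves some room to read the 5-minute score as worst pain. A simulation with assumed group means of 50 and 35 mm and SD 26 found that rounding to whole points would alter the significance call in about 2.5% of trials.

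What stands is that the label is wrong and is in current text. The rest carries little weight:

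- The 2.5% needs a rounding step that the protocol nowhere describes.
- The documents do not give the other sites' scales or detailed pooling rules, so nothing shows that this label would reach the meta-analysis. A site reporting the millimetre outcome it has defined supplies millimetres.
- The Primary Aim is general. The outcome definition is specific and ties the score to a moment 5 minutes after speculum removal, which describes pain at that time better than the day's maximum. The table that describes the outcomes may say so outright, so its absence from the text available cannot be counted as a gap.
- Naming worst pain as a secondary outcome would add something that Secondary Outcomes does not list.

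**Conclusion.** This is a clerical slip with no consequence for the design or the result. The definition, the SD, the design difference and the meaningful difference all fix a 100-mm scale, and the forms' unnumbered lines fit it even though they print no length. An analyst working from the protocol would measure the marks in millimetres and run the stated t-test. N stays at 96 and power at about 80%, and the p-value is the same in either unit. Even a literal reading with rounding would cost about 0.5 percentage points of power.

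The choice between the two 5-minute lines is at most missing detail, which a look at Table 1 may settle and which a sensible reading already fills with current pain. The conclusion assumes a two-sided test, which the reproduced sample size supports, and that the recorded lines are measured in millimetres, as the outcome definition says. The phrase can be tidied whenever the document is next edited, but nothing depends on it.
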